17.0 Confidentiality of Data

1. To maintain the confidentiality of the data:
 - I will use a unique study identifier to code individuals' identifiable data and will store the master list separate from the study data.
 - I will use a unique study identifier to code individuals' data, but it will never be linked to a master list.
 - Other- please explain: Click here to enter text.

Provide a plan to maintain or destroy identifiers once analysis of identifiable information is complete. Data will be retained for five years publication of the findings or all required final reports (e.g., progress and financial) for the project have been submitted to NIH (45 CFR Parts 75.361 and 75.364).

2. How are you storing your electronic data?

- CWRU Redcap
- CWRU Secure Research Environment (SRE)
- CWRU Box
- OnCore
- CWRU Secure Network Drive
- Other - List storage method and provide justification: Click here to enter text.

Please note: if you're storing or entering your electronic data in any system other than an approved system listed above, please contact the CWRU IRB ([contact]).

3. I acknowledge that paper research data and documents will be stored in a double-locked secure environment in the following **location**: Click here to enter text.
 - We will not have paper research documents.

4. Will data be shared?

- Yes
 - List the exact data elements that will be shared: Click here to enter text.
 - Describe how data will be sent: Click here to enter text.
- No
- N/A

(Please note: if sharing data, please contact the CWRU Tech Transfer Office to ensure the proper contracts/agreements are in place.)

18.0 HIPAA Authorization

Does this study collect, access, use, or distribute any Protected Health Information (PHI)?
Protected Health Information (PHI) is (1) any individually identifiable health information transmitted or maintained in a medical record, paper or electronic, or (2) designated data set that was created, disclosed, or used in the course of providing a health care service such as diagnosis, payment or treatment.

Yes No

If yes, indicate how HIPAA authorization will be obtained (check all that apply):

- HIPAA authorization is in the consent form
- I am receiving a Limited Data Set under a Data Use Agreement (DUA)
- Requesting a full or partial waiver of HIPAA for prescreening
 - I will complete the Request for Waiver of HIPAA Authorization form. *See SpartaIRB Library*
- Requesting a full or partial waiver of HIPAA
 - I will complete the Request for Waiver of HIPAA Authorization form. *See SpartaIRB Library*

19.0 Risks to Research Participants

1. List the reasonably foreseeable risks such as breach of confidentiality, discomforts, hazards, or inconveniences to the research participants related to their participation in the research. Include a description of the probability, magnitude, duration, and reversibility of the risks. Include the physical psychological, social, legal, and economic risks.
There are no anticipated physical risks associated with this study. However, there is always a rare risk of a data breech. There is the rare potential for psychological distress related to some of the questions asked in the survey (drug, alcohol and distress questions).
2. If applicable, indicate which experimental procedures may have risks to the research participants that are currently unforeseeable. [Click here to enter text.](#)
 N/A
3. If applicable, describe the risks to others who are not research participants. [Click here to enter text.](#)
 N/A
4. Describe the availability of medical or psychological resources that research participants might need. Since participants are being recruited from a wider geographic area national resources such as the National Suicide Prevention Lifeline, Crisis Text Line, SAMHSA's National Helpline will be provided if they do not have a healthcare provider.
 N/A

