4.0 Inclusion and Exclusion Criteria

Directions: Describe how individuals will be screened for eligibility.

Participants will self-identify inclusion into the study based on the following parameters listed below

Using the tables below, describe the inclusion and exclusion criteria that will define who will be included and excluded in your final study sample.

	Inclusion
1.	Age range: from 18 to 25 years
2.	Have been diagnosed with T1D for at least 6 months
3.	Have no other major health problems (e.g., chronic medical condition or major psychiatric illness)

4.	Are not currently participating in any intervention studies
5.	Read/speak English

Exclusion	
1.	Previous obstructive sleep apnea (OSA) diagnosis
2.	Current pregnancy
3.	Night shift workers
4.	High risk score on the Berlin Questionnaire (aim 4 only)
5.	Clinically significant insomnia – scores ≥ 15 on the Insomnia Severity Index (aim 4 only)

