identified prior to data-analysis. All transcripts will be organized and coded with NVivo 12 for Mac. An audit trail will be used to track decision-making and triangulate the data. Interview data were analyzed and coded for themes using qualitative content analysis. The analysis will be inductive and begin during the data collection process to allow for ongoing modification of the interview guide. Interviews will be coded using an *in vivo* approach. Sampling will continue until redundancy is reached. 3) REDCap will be used to monitor completion of the surveys. An RA will monitor participants during the interview for aim 4 for any signs of distress. Participants will be referred to a mental health clinician or the diabetes health care provider if they have any of these concerns. If new or exacerbated health problems, such as sleep apnea or emotional distress, are detected during the study assessments, participants will be referred to their current providers (or a provider of their choice) for follow-up evaluation and possible treatment. If participants do not have an existing healthcare provider, a list of providers in the area will be provided. If safety is a concern, such as loss of consciousness with hypoglycemia during an interview session, the emergency medical response system will be activated and the RA will stay with the participant until emergency medical services arrive. 4) N/A all data will be self-report and medical records will not be queried. Participants will be asked to share their continuous glucose monitor reports or Dexcom share codes in a secure file location in REDCap and the files will be de-identified prior to analysis in SPSS or REDCap. 5) N/A no devices are being used for this study.

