20.0 Provisions to Protect the Privacy Interests of Research Participants

Directions: Describe the steps that will be taken to protect research participants' privacy interests. (consider issues such as physical space, proximity to other, and participant preferences)

This research is covered by a certificate of confidentiality. Effective October 1, 2017, all NIH funded research that was commenced or ongoing on or after December 13, 2016 and collects or uses identifiable, sensitive information is deemed to be issued a Certificate of Confidentiality and is therefore required to protect the privacy of individuals who are subjects of such research in accordance with subsection 301(d) of the Public Health Service Act. Under the new policy, the NIH funded researchers will no longer have to request a Certificate of Confidentiality, nor will they receive an actual certificate. No identifiers will be linked with survey responses. All data once de-identified will be maintained on a secure password protected research drive. There is the rare potential for psychological distress related to some of the questions asked in the survey (alcohol, drug use, and distress questions). Information about how to access clinic support services related to psychological risks will be provided on the consent form.

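### The three national crisis lines should be offered to every participant, not tied to lacking a healthcare provider

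*Protocol*

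**What the plan says.** Protocol section 19.0 identifies the risk: "There is the rare potential for psychological distress related to some of the questions asked in the survey (drug, alcohol and distress questions". Asked what medical or psychological resources are available, the same section notes that recruitment covers a broad area, lists three national lines (a suicide lifeline, a crisis text line and the SAMHSA helpline), and ends: "National Helpline will be provided if they do not have a healthcare provider".

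Two other places bear on support. Section 20.0 states: "Information about how to access clinic support services related to psychological risks will be provided on the consent form". Section 12.0 states: "If new or exacerbated health problems, such as sleep apnea or emotional distress, are detected during the study assessments, participants will be referred". The referral is to the participant's existing provider or another of their choice, and people without one receive a list of local providers.

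On monitoring, section 12.0 says "REDCap will be used to monitor completion of the surveys", and has a research assistant watch for distress during the Aim 4 interview. The SAP says nothing on this point.

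**The concern.** The condition in section 19.0 selects people by whether they have a provider, while the risk it answers comes from survey questions put to everyone in Aims 1-3. A participant who is upset by a distress, alcohol or drug question at home, at any hour, needs something that can be reached at once. A crisis line does that; a routine provider generally does not. Inclusion requires "Have been diagnosed with T1D for at least 6 months", so most participants probably have a provider (an inference; the documents do not say), and for many it will be the one who treats their diabetes. Read literally, the rule promises the lines to what is probably the smaller part of the sample. What is at stake is participant safety; no estimate or test is affected.

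**Working it through.** No arithmetic applies and the plan gives no figure to reproduce. The check sets the protocol sections side by side.

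1. **Who is exposed.** Recruitment is through websites and social media (8.0), all surveys run in REDCap (12.0), and interviews are by video call (9.0). Section 19.0 places the risk in the survey. Exposure is therefore the whole Aims 1-3 sample of 200-300 (5.0), although participants may skip questions (10.0).

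2. **Who is promised the lines.** Under 19.0, those without a provider. The word *only* is not in the text, but it is the plain reading of the condition, and no other section extends the lines to everyone.

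3. **What people with a provider are promised.** Referral on detection (12.0), and consent-form information on clinic support services (20.0). The second applies to every participant.

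4. **Whether these cover immediate crisis support.** Only in part. Referral starts from a detected problem. For the Aims 1-3 surveys the stated monitoring is of completion, and a person watches for distress only in Aim 4. Distress caused by a question also need not show up as a high score. The section 20.0 information concerns clinic services, and no study clinic is described for this remotely recruited sample. Whether the consent form also lists the crisis lines cannot be checked.

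5. **What counts as detected.** Aim 1 (2.0) measures four conditions: emotional distress, diabetes distress, high-risk sleep apnea and insomnia. Section 4.0 gives criteria for two of them: "High risk score on the Berlin Questionnaire (aim 4 only") and a score of at least "15 on the Insomnia Severity Index (aim 4 only"). The Aim 4 label limits the exclusion. The same categories appear in Aim 1, so the natural reading is that they carry the same definitions there. That leaves 4 - 2 = 2 conditions, the two distress measures, with no stated cut-off, and no sentence linking any of the four to the referral in 12.0.

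Steps 1 and 2 establish the main point: exposure is universal and the promise is conditional. Step 3 limits it. Step 5 is a gap in detail.

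**The case against.** The strongest reply is that sections 12.0 and 19.0 form a tiered plan. People with a provider are referred to that provider; people without one get a local list or, because recruitment is wide, national lines. On this reading geography explains why the fallback is national, and lacking a provider explains who needs a fallback. That is a coherent rationale and it stands. A reader might infer that the condition has no reason behind it; the documents do not support that.

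A reader might also infer that participants with a provider are left without support. They are not: sections 12.0 and 20.0 both cover them, and the consent form may already show the lines.

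What the reply does not answer is timing. A tier that begins with referral to a provider suits a health problem found on assessment. It suits acute distress while answering a survey alone less well, and nothing is gained by withholding three telephone or text contacts from people who have a provider.

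**Conclusion.** The point holds in a limited form. Section 19.0 ties the three national lines to lacking a provider although the survey risk is common to all Aims 1-3 participants, and removing the condition is a specific safety gain at almost no cost. It rests on two judgements: that a routine or diabetes provider does not replace immediate crisis support, and that the condition means what it plainly says.

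Its size cannot be put as a number. One could multiply an assumed provider share by enrolment: at 50%, 0.50 × 200 = 100 to 0.50 × 300 = 150 people; at 99%, 0.99 × 200 = 198 to 0.99 × 300 = 297. This counts people who have a provider, not people harmed or unsupported, and section 19.0 calls the distress risk rare. It should not be used as a measure of harm.

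A reader might further infer that people who screen positive in Aims 1-3 will not be told. Section 12.0 says they will be referred. That the starting rule is unwritten is an operational gap, not evidence that they go uninformed. It warrants a minor clarification only.

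**What to change.** **Main change.** In section 19.0, delete the condition about having no provider, and state that the three lines are shown to all participants in the consent form and on the completion page of the baseline survey. The consent form also reaches those who stop before that page. In section 20.0, add the three lines to the promised information on clinic support services. Do not replace that information, since doing so would remove non-crisis support now promised to everyone. The cost is a consent form modification and the text of one survey page.

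**Optional clarification.** In section 12.0, state that for Aims 1-3 a problem is detected when a participant meets an Aim 1 category: Berlin high risk, Insomnia Severity Index of 15 or more, or the emotional-distress or diabetes-distress cut-off used for prevalence, and state those two cut-offs. Deliver the result as an automatic on-screen message at survey completion, saying that it is a screening result and not a diagnosis and advising follow-up with a provider. No staff member then has to connect scores to names, which fits the commitment in section 20.0 to keep identifiers apart from survey answers. The costs are building and testing the scoring in REDCap, some worry or provider visits from false-positive screens, and the possibility that a sleep message shown at baseline influences the diary week that follows.

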20.0 Provisions to Protect the Privacy Interests of Research Participants

Directions: Describe the steps that will be taken to protect research participants' privacy interests. (consider issues such as physical space, proximity to other, and participant preferences)

This research is covered by a certificate of confidentiality. Effective October 1, 2017, all NIH funded research that was commenced or ongoing on or after December 13, 2016 and collects or uses identifiable, sensitive information is deemed to be issued a Certificate of Confidentiality and is therefore required to protect the privacy of individuals who are subjects of such research in accordance with subsection 301(d) of the Public Health Service Act. Under the new policy, the NIH funded researchers will no longer have to request a Certificate of Confidentiality, nor will they receive an actual certificate. No identifiers will be linked with survey responses. All data once de-identified will be maintained on a secure password protected research drive. There is the rare potential for psychological distress related to some of the questions asked in the survey (alcohol, drug use, and distress questions). Information about how to access clinic support services related to psychological risks will be provided on the consent form.

21.0 Potential Benefit to Research Participants

There is potential benefit to research participants.

Describe the potential benefits that individual research participants may experience from taking part in the research. Include the probability, magnitude, and duration of the potential benefits. *Do not list compensation. Click here to enter text.*

There is no direct benefit to research participants.

If no direct benefit, state the potential benefit to society or others. *Do not list compensation.* There is no direct benefit to participants from participating in this study; however, data from this study could be used to develop meaningful interventions to improve sleep and potentially diabetes related outcomes (glycemic control, decreased symptoms, improved self-management and prevention of premature complications).

22.0 Withdrawal of Research Participants

Directions: Describe the anticipated circumstances under which research participants will be withdrawn from the research without their consent. Also include the procedures that will be followed when a research participant withdraws or are withdrawn from the research, including partial withdrawal from procedures with continued data collection.

Participation is voluntary. If a choice is made not to participate, participants will be notified that it will not affect current or future relations with the University. There is no penalty or loss of benefits for not participating or for discontinuing participation. Participants will be notified that they are free to withdraw from the study at any time. **If they do decide to withdraw from the study they will be encouraged to notify the research team immediately.** The research team may also end participation in this study if instructions are not followed, scheduled responses are missed, or if safety or welfare are at risk. Partial data will still be used in the analysis.

N/A

23.0 Alternatives to Participation

Directions: List other options to participation. If subjects will be compensated with extra course credit, the course instructor offering extra course credit must provide alternatives to earn extra course credit. The alternative assignment must require equal or less time and effort for the same amount of earned extra credit that you can earn through participation in research. If there are other available clinical treatments, what would be included if a

subject continued on standard of care therapy. If there is a viable alternative you must list it in the consent.

[Click here to enter text.](#)

The alternative is for research subjects not to participate.

24.0 Costs to Research Participants

There are no costs to research participants or their insurance companies (there are no clinical visits or billable procedures.) – *please leave rest of this section blank*

1. Describe what costs research participants will be responsible for as a result of their participation in the research, including but not limited to: clinical services required by the protocol deemed billable to insurance, transportation to study visits, parking, costs of drugs, cost of therapy, lost broken or stolen devices, etc. No associated costs
2. Explain who will be responsible for payment of provided services in the event of insurance denials. N/A
3. List what procedures, drugs, devices, supplies will be paid by the study sponsor or covered by other funding. List the other funding source. No services will be covered

25.0 Research Participant Compensation

There is no compensation or reimbursement for research participants – *please leave rest of this section blank*

There is compensation for research participants.
 Describe the schedule, payment method, and payment total of any incentives or compensation that research participants will receive for participation in the research (e.g., gift cards or cash with amount, t-shirts, devices, bags, swag, etc.) Eligible participants completing the survey and diaries will receive up to two \$10 Amazon gift cards (up to \$20), one \$10 gift card for the completion of the baseline survey and one \$10 gift card for the completion of the sleep diaries (aims 1-3). Participants will receive an incentive Amazon gift card payment of \$40 for participating in aim 4 (focused interview on zoom).
 There will be reimbursement for research participants.
 Describe the schedule, payment method, and payment total of any reimbursement that research participants will receive for participation in the research (e.g., gift cards or cash with amount, etc.) [Click here to enter text.](#)

26.0 Compensation for Research Related Injury

Describe who will pay for the costs of medical treatment and/or compensation in the event of a research related injury:

- Funding agency is providing some/all payment for injury
- Funding agency is providing no payment for injury
- N/A

27.0 Provisions to Monitor the Data to Ensure the Safety of Research Participants

1. Describe how often the data will be monitored for completeness, accuracy and adherence to the protocol. N/A this is a cross sectional design. Data will be collected once for aims 1-3 and once for aim 4 as this is not a repeated measures design.
2. Indicate if there will be a Data and Safety Monitoring Board or Committee:
 - There will not be a formal Data and Safety Monitoring Board/Committee.
 - There will be a formal Data and Safety Monitoring Board/Committee.

Provide information about the DSMB/C including the contact information of the committee member(s) (as applicable); whether it is independent from the study sponsor; how often it meets; the type of data that will be used; written reports, etc. Click here to enter text.

28.0 Additional Information

If you have any additional information regarding your study not covered in the template, please include it here. Click here to enter text.

29.0 Devices

Does the study include the use of a device that is integral to the study question?

- Yes - Answer the questions below.
- No - Leave the rest of this section blank.

There is an active IDE (Investigational Device Exemption) for the proposed study. [Attach an official letter of support or proof of approval which identifies the IDE holder and IDE number to the SpartaIRB smartform.](#)
List devices: Click here to enter text.

The device has obtained a 501k clearance. [Attach 501k documentation to the SpartaIRB smartform.](#)
List devices: Click here to enter text.

The device meets the criteria for an IDE Exemption. [Download the IDE Exemption Form from the SpartaIRB library \(HRP-580\) and attach to the SpartaIRB smartform.](#)
List devices: Click here to enter text.

The device (and its use) is a non-significant risk device for the proposed study design. List devices here and provide the PI's rationale for the non-significant risk device determination. Click here to enter text.

If the research involves device(s), describe your plans to use, store, handle, administer and track those device(s) to ensure that they will be used only on research participants and be used only by authorized investigators. [Click here to enter text.](#)

